# **Table 3 Estimation of PK Parameters**

Dar	1	A	T.	Æ	
Dav		Α	. 13	/1	:

PK Parameter	Definition
C max	Maximum observed plasma drug concentration (ng/mL), obtained
	directly from the observed concentration versus time data.
t max	Time to reach maximum plasma concentration (h), obtained directly from
	the observed concentration versus time data.
AUC (0-last)	Area under the concentration-time curve from time 0 until the last
	quantifiable concentration (ng·h/mL), calculated by linear up/log down
	trapezoidal summation.
AUC (0-inf)	Area under the concentration-time curve from time 0 extrapolated to
	infinity (ng·h/mL), calculated by linear up/log down trapezoidal
	summation and extrapolated to infinity by addition of the last
	quantifiable observed concentration divided by the elimination rate
	constant: $AUC_{(0-last)} + C_{last}/\lambda_z$ .
$\lambda_{Z}$	Apparent terminal elimination rate constant (1/h), determined by linear
	regression of the terminal points of the log-linear concentration-time
	curve. The Best Fit method utilized by WinNonlin will be used to identify
	the terminal linear phase of the concentration-time profile, with visual
	assessment and adjustment of the selected data points by the PK scientist
	if warranted. A minimum of 3 data points will be used for determination.
t 1/2	Apparent terminal elimination phase half-life (h), determined as $ln2/\lambda_Z$ .
CL/F	Apparent systemic clearance after extravascular dosing (L/h), calculated

Document: PK/PD STATISTICAL ANALYSIS PLAN

Author: [name] Version Number:

1.0 12 Aug 2019

Template No: CS\_TP\_BS016 – Revision 5 Reference: CS\_WI\_BS005

Effective Date: 01Apr2018

 $Copyright © 2009, 2010, 2012, 2016, 2018 \ IQVIA. \ All \ rights \ reserved. \ The \ contents \ of \ this \ document \ are \ confidential \ and \ proprietary \ to \ IQVIA \ Holdings \ Inc. \ and \ its \ subsidiaries. \ Unauthorized \ use, \ disclosure \ or \ reproduction \ is \ strictly \ prohibited.$ 

Version Date:

Palladio BiosciencesInsert Customer Name/Logo PK/PD STATISTICAL ANALYSIS PLAN: PROTOCOL PA-102 Page 27 of 39

PK Parameter	Definition	
	as (lixivaptan only):	
	
 
Day 1 AM: dose divided by AUC(0-inf), or
 
	
	
 
Day 7 AM: dose divided by AUC(0-last).
 
	
V z /F	Apparent volume of distribution following extravascular dosing (L), calculated as CL/F divided by $\lambda_Z$ (lixivaptan only).	

### Day 1 PM:

PK Parameter	Definition
C max	Maximum observed plasma drug concentration (ng/mL), obtained
	directly from the observed concentration versus time data.
t max	Time to reach maximum plasma concentration (h), obtained directly from
	the observed concentration versus time data.
AUC (0-last)	Area under the concentration-time curve from time 0 until the last
	quantifiable concentration (ng·h/mL), calculated by linear up/log down
	trapezoidal summation.

Document: PK/PD STATISTICAL ANALYSIS PLAN

Author: [name] Version Number: 1.0 Version Date: 12 Aug 2019

Template No: CS\_TP\_BS016 - Revision 5 Reference: CS\_WI\_BS005

Effective Date: 01Apr2018

Palladio BiosciencesInsert Customer Name/ Logo PK/PD STATISTICAL ANALYSIS PLAN: PROTOCOL PA-102 Page 28 of 39

Day 7 AM:			
PK Parameter	Definition		
C max	Maximum observed plasma drug concentration (ng/mL), obtained		
	directly from the observed concentration versus time data.		
$t_{max}$	Time to reach maximum plasma concentration (h), obtained directly from		
	the observed concentration versus time data.		
$AUC_{(0-last)}$	Area under the concentration-time curve from time 0 until the last		
	quantifiable concentration (ng·h/mL), calculated by linear up/log down		
	trapezoidal summation.		
CL/F	Apparent systemic clearance after extravascular dosing (L/h), calculated		
	as (lixivaptan only):		
	
 
Day 1 AM: dose divided by AUC(0-inf), or
 
		
	
 
Day 7 AM: dose divided by AUC(0-last).
 
		
V z /F	Apparent volume of distribution following extravascular dosing (L),		
	calculated as CL/F divided by $\lambda_{\text{Z}}$ (lixivaptan only).		
$RC_max$	Accumulation ratio for $C_{\text{max}}$ , calculated as (lixivaptan only):		
	[C max on Day 7]/[C max on Day 1].		
RAUC (0-last)	Accumulation ratio for AUC (0-last) , calculated as (lixivaptan only):		
	$[AUC_{(0-last)} \text{ on Day 7}]/[AUC_{(0-last)} \text{ on Day 1}].$		

Document: PK/PD STATISTICAL ANALYSIS PLAN Author: [name]

ithor: [name] Version Number:

Version Date:

1.0 12 Aug 2019

Template No: CS\_TP\_BS016 – Revision 5 Reference: CS\_WI\_BS005

Effective Date: 01Apr2018

Palladio BiosciencesInsert Customer Name/ Logo PK/PD STATISTICAL ANALYSIS PLAN: PROTOCOL PA-102 Page 29 of 39

PK Parameter	Definition
C max	Maximum observed plasma drug concentration (ng/mL), obtained
	directly from the observed concentration versus time data.
t max	Time to reach maximum plasma concentration (h), obtained directly from
	the observed concentration versus time data.
AUC (0-last)	Area under the concentration-time curve from time 0 until the last
	quantifiable concentration (ng·h/mL), calculated by linear up/log down
	trapezoidal summation.
AUC (0-14)	Area under the concentration-time curve from time 0 until 14 hours post-
	dose (ng·h/mL), calculated by linear up/log down trapezoidal summation.
	Actual elapsed time for the nominal 14-hour sample will be used for the
	calculation. If the time deviation at 14 hours is larger than $\pm 15.0\%$ , then
	AUC (0-14) will only be listed for that profile and excluded from
	statistics/summaries.
$\lambda_z$	Apparent terminal elimination rate constant (1/h), determined by linear
	regression of the terminal points of the log-linear concentration-time
	curve. The Best Fit method utilized by WinNonlin will be used to identify
	the terminal linear phase of the concentration-time profile, with visual
	assessment and adjustment of the selected data points by the PK scientist
	if warranted. A minimum of 3 data points will be used for determination.
t 1/2	Apparent terminal elimination phase half-life (h), determined as ln2/ $\lambda_Z$ .
$MRC_{max}$	Ratio of metabolite $C_{\text{max}}$ to parent lixivaptan $C_{\text{max}}$ , calculated for all
	metabolites and corrected for molecular weight of metabolite and parent

Document: PK/PD STATISTICAL ANALYSIS PLAN

Author: [name] Version Number: 1.0

Version Date: 12 Aug 2019

Template No: CS\_TP\_BS016 – Revision 5 Reference: CS\_WI\_BS005

Effective Date: 01Apr2018

Palladio BiosciencesInsert Customer Name/ Logo PK/PD STATISTICAL ANALYSIS PLAN: PROTOCOL PA-102 Page 30 of 39

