3 INVESTIGATIONAL PLAN

3.1 Study Design

This is a Phase 2, open-label, parallel-group, multiple dose study designed to evaluate the PK, PD, safety, and tolerability of multiple BID doses of 50 and 200 mg lixivaptan in ADPKD subjects with chronic kidney disease in stages CKD1, CKD2 or CKD3. The study will be conducted at multiple Clinical Research Units (CRUs) in the United States (US).

For all subjects, this study includes a Screening period of 42 days (Day -44 through Day -3), i.e. up to 44 days prior to dosing on Day 1. Subjects will be confined to the CRU on two separate occasions, with a total period of confinement of up to 7 days and 5 nights. The first confinement period will last up to 4 days (up to 3 nights). Subjects will be admitted to the CRU in the afternoon of Day -2 or, depending on travel arrangements, in the morning of Day -1, and will be domiciled until discharge from the CRU in the morning of Day 2. The second confinement period will last 3 days (2 nights). Subjects will return to the CRU to be admitted in the afternoon of Day 6 and will be discharged from the CRU in the morning of Day 8. Alternatively, subjects may be offered the option to remain admitted to the CRU for the entire duration of the dosing period, i.e. from the initial admission on Day -2 (or Day -1 where applicable) until discharge on Day 8.

Except for the AM and PM doses on Days 1, 6, and 7, and the AM doses on Days 2, 4 and 6, all other doses will be self-administered by the subject. Subjects will be required to record self-administered doses in a Study Dosing Diary (Section 5.7.1).

Enrolled subjects will be assigned according to CKD classification to take one of 2 dose regimens (Table 5-1) for 7 days. Each dose regimen includes morning (AM) and evening (PM) oral administration of lixivaptan. Doses will be administered with approximately 10 hours separation between the AM and PM doses as follows. When subjects are confined to the CRU, the PM dose will be administered 10 ± 0.25 hours after the AM dose. When lixivaptan is self-administered, the PM dose will be administered 10 ± 1.0 hours after the AM dose. Subjects will maintain adequate hydration throughout the study by adhering to a predetermined daily fluid intake regimen (Section 5.9).

To be enrolled, subjects must meet the following diagnostic criteria for ADPKD (modified Pei-Ravine criteria):

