5.3 Treatments Administered

Subjects assigned to one of the 2 dose levels of lixivaptan (Table 5-1) will receive oral lixivaptan BID (AM and PM) from Day 1 through Day 7. The PM dose will be administered approximately 10 hours after the AM dose.

Table 5-1 Study Cohorts and Lixivaptan Dose Levels

Cohort	CKD stage	Dose*	N	
1	CKD1 or CKD2	200 mg BID	8 subjects	Candidate maximum tolerated dose
2	CKD3	200 mg BID	8 subjects	
3	CKD1 or CKD2	50 mg BID	8 subjects	Candidate lowest effective dose
4	CKD3	50 mg BID	8 subjects	

*PM dose to be administered approximately 10 hours after the AM dose

Prior to the morning doses on Days 1 and 7, subjects will fast overnight for ≥ 8 hours prior to study medication administration. Water will be allowed *ad libitum* during the overnight fasting. Liquids (other than water) are considered part of the ≥ 8 hour overnight fast.

In the morning of Days 1 and 7, subjects will receive lixivaptan with room temperature water (approximately 240 mL [8 ounces]) and will remain fasted for 2 hours after dosing. Water

will be allowed *ad libitum* during the 2 hours fasting, however subjects will be required to abstain from consuming other liquids until 2 hours after dosing.

The evening doses on Days 1 and 7 will be administered in the CRU under fasting conditions, i.e. 2 hours before and 2 hours after meals. Liquids (other than water) are considered part of the 2 hour fast.

Study drug will be administered orally to subjects. Administration of each dose of study drug while the subject is confined at the CRU will be supervised, verified, and documented according to the CRU's standard operating procedures. A mouth and hand check will be performed immediately after study drug administration.

The actual date and time of each dose administration will be entered in the eCRF.

When not confined to the CRU, subjects will self-administer lixivaptan with water (approximately 240 mL) and without fasting. Subjects will continue to adhere to the recommended fluid intake regimen outlined in [Section 5.9](#).

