7.1 Pharmacokinetic Parameters

The following PK parameters will be calculated using noncompartmental methods, whenever possible, based on lixivaptan and lixivaptan metabolite (WAY-141624, WAY-138451, and WAY-138758) concentrations, and at the timepoints shown in [Table 12-1](#):

PK Day 1 (AM Dose)

PK Parameter	Definition
C_{\max}	maximum observed plasma drug concentration
t_{\max}	time to reach maximum plasma concentration
AUC_{0-t}	area under the concentration-time curve from time 0 until the last quantifiable concentration, calculated using the linear trapezoidal rule for increasing values, and the log trapezoidal rule for decreasing values
$AUC_{0-\infty}$	area under the concentration-time curve extrapolated to infinity, calculated as: $AUC_{0-\infty} = AUC_{0-t} + C_t/\lambda_z$
λ_z	apparent terminal elimination rate constant
$t_{1/2}$	terminal elimination phase half-life, calculated as $\ln(2)/\lambda_z$
CL/F	total body clearance, calculated as $Dose/AUC_{0-\infty}$ (lixivaptan only)
V_z/F	volume of distribution, calculated as $CL/F/\lambda_z$ (lixivaptan only)

PK Day 1 (PM Dose) – Study Day 1 - 2

PK Parameter	Definition
C_{\max}	maximum observed plasma drug concentration
t_{\max}	time to reach maximum plasma concentration
AUC_{0-t}	area under the concentration-time curve from time 0 until the last quantifiable concentration, calculated using the linear trapezoidal rule for increasing values, and the log trapezoidal rule for decreasing values

Day 7 (AM Dose)

PK Parameter	Definition
C_{max}	maximum observed plasma drug concentration
t_{max}	time to reach maximum plasma concentration
AUC_{0-t}	area under the concentration-time curve from time 0 until the last quantifiable concentration, calculated using the linear trapezoidal rule for increasing values, and the log trapezoidal rule for decreasing values
CL/F	total body clearance, calculated as Dose/ AUC_{0-last} (lixivaptan only)
Vz/F	volume of distribution, calculated as CL/F/ λ_z (lixivaptan only)

Day 7 (PM Dose)

PK Parameter	Definition
C_{max}	maximum observed plasma drug concentration
t_{max}	time to reach maximum plasma concentration
AUC_{0-14}	area under the concentration-time curve from time 0 until 14 hours postdose
AUC_{0-t}	area under the concentration-time curve from time 0 until the last quantifiable concentration, calculated using the linear trapezoidal rule for increasing values, and the log trapezoidal rule for decreasing values
λ_z	apparent terminal elimination rate constant

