Day 2, 4 and 6: 0 hours (immediately before AM dose);
Day 7: 0, 1, 2, 4, 6, 9, 10, 11, 12, 14, and 16 hours post AM dose. The collections at 0 and 10 hours are immediately before the AM and PM doses, respectively;
Day 8: 0 hours (corresponding to 24 hours after AM dose on Day 7) and 10 hours (corresponding to 24 hours after PM dose on Day 7);
Day 9: 48 hours after PM dose on Day 7;
Day 11: 96 hours after PM dose on Day 7.
- ¹⁴ Urine will be collected for determination of spot urine osmolality and urine specific gravity at the following timepoints:
Day -1: 0 (start), 1, 2, 4, 6, 9, 10, 11, 12, and 14 hours.

Day 1: 0, 1, 2, 4, 6, 9, 10, 11, 12, and 14 hours post AM dose. The collections at 0 and 10 hours are immediately before the AM and PM doses, respectively;

Day 2: 0 hours (immediately before AM dose on Day 2, corresponding to 24 hours after AM dose on Day 1).

Day 7: 0, 1, 2, 4, 6, 9, 10, 11, 12, and 14 hours post AM dose. The collections at 0 and 10 hours are immediately before the AM and PM doses, respectively;

Day 8: 0 hours (corresponding to 24 hours after AM dose on Day 7).

Note: Subject may not be able to void at all timepoints - see [Section 6.1.7](#). For all voids, the volume (mL) and the date and time of void will be recorded.

- ¹⁵ Record daily urine output on Day -1, Day 1 and Day 7. On Day -1, measurement will begin 24 hours before the expected time of first study medication on Day 1 AM. On Day 1 and Day 7, measurements will begin immediately before the AM dose and will continue for 24 hours into the morning of Day 2 and Day 8, respectively.
- ¹⁶ Blood samples for determination of plasma copeptin will be taken at approximately the same time of day (in the morning and, on dosing days, before the lixivaptan dose).
- ¹⁷ Subjects will be admitted to the CRU in the evening of Day -2 or in the morning of Day -1. For subjects admitted to the CRU on Day -2, the Screening period will be until Day -3. For subjects admitted to the CRU on Day -1, the Screening period will be until Day -2.

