12.3 Appendix 3: Assessment Windows

Table 12-2 Assessment Windows

Procedure	Dosing Day	Window (units)
Lixivaptan PM dose	Day 1 – Day 7	In CRU: 10 hr ± 15 minutes after AM dose Self-Administered: 10 hr ± 1 hr after AM dose
	Assessment Day	
PK Blood Samples	Day 1, Day 2, Day 4, Day 6, Day 7, Day 8, Day 9, Day 11	- 60 minutes (predose Day 1) - 10 minutes (predose Day 7) ± 3 min (≤4 hr) ± 5 min (> 4 hr but ≤ 12 hr) ± 10 min (> 12 hr but ≤ 24 hr) ± 1 hr (> 24 hr but ≤ 48 hr) ± 2 hr (> 48)
Urine Osmolality and Urine Specific Gravity	Day 1-2, Day 7-8	Subjects will empty their bladders completely 15 ± 5 minutes prior to each scheduled collection, after which they will have 30 minutes to provide a spot urine sample. Subjects who will not be able to provide a sample within 30 minutes will be given an additional 30 minutes to do so and the different sampling time will be recorded.
Electrocardiogram	Screening, Day 1, Day 8	- 60 minutes (predose), ± 30 minutes (postdose)
Vital Signs	Screening, Day -1, Day 1, Day 2, Day 4, Day 6, Day 7, Day 8, Day 35	- 60 minutes (predose), ± 30 minutes (postdose)
Clinical Laboratory Samples	Screening, Day -1, Day 2, Day 7, Day 35	- 60 minutes (predose Day 2 and Day 7) In the morning on Day -1 and Day 35
Tolerability Questionnaire	Day 2, Day 7	Subjects will complete the questionnaire in the morning of Day 2, before discharge from the CRU, and in the morning of Day 7.
TKV and LV (MRI)	Baseline End of dosing End of study	Baseline: between Screening and Day -1 End of dosing: Day 7 or 8 or 9 End of study: Day 35 ± 2

Table abbreviations: hr = hours, PK= pharmacokinetic

Summary of Changes in the Conduct of the Study (from Section 9.8.1 of the Clinical Study Report, dated September 22, 2020)

Changes in the Conduct of the Study

There were 2 protocol versions that were not implemented or submitted to the IRB. Protocol versions 1 and 2 were marked final and dated 19 March 2018 but the version number 1.0 remained unchanged in the footer of both versions. Refer to Note to File (dated 23 February 2020) in Appendix 16.1.1 to distinguish between the 2 documents.

Protocol version 3 (dated 24 April 2018) was the first protocol version submitted to the IRBs and amended. There were 2 subsequent protocol amendments, versions 4 and 5, that were implemented after the first subject was enrolled. Copies of the protocol and protocol amendments are provided in Appendix 16.1.1. Brief summaries of the changes are outlined below.

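### Day 7 CL/F divides one dose by the AUC of the 10-hour AM interval; under 10 h/14 h dosing this overstates CL/F and Vz/F, by up to about 20%

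*SAP*

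**What the plan says.** - PK/PD SAP 14.2, Table 3, Day 7 AM: clearance is "Day 7 AM: dose divided by AUC", the AUC being AUC(0-last) for that dosing interval. Protocol 7.1, Day 7 AM, agrees: "total body clearance, calculated as Dose/ AUC_{0-last} (lixivaptan only").
- The same SAP table gives Day 7 AM Vz/F as "calculated as CL/F divided by" λz. SAP Table 5 and protocol 7.1 list λz for Day 1 AM and Day 7 PM, but not for Day 7 AM.
- Protocol 5.3, footnote to Table 5-1: "PM dose to be administered approximately 10 hours after the AM dose". The in-clinic window in protocol Table 12-2 is "In CRU: 10 hr ± 15 minutes after AM dose". The next AM dose therefore falls about 14 h after the PM dose.
- Protocol Table 12-1, footnote 13, sets the samples: "Day 7: 0, 1, 2, 4, 6, 9, 10, 11, 12, 14, and 16 hours post AM dose". The 10 h draw comes just before the PM dose. The Day 8 0 h draw is 24 h after the AM dose, so 14 h after the PM dose.
- Day 1 clearance has a different basis: dose divided by AUC(0-inf).
- AUC(0-14) is already planned for Day 7 PM.

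**The concern.** Because the AM profile stops at the PM dose, Day 7 AUC(0-last) is in effect AUC(0-10). In an unequally spaced regimen, neither single interval carries exactly one dose's worth of AUC; the identity holds only over the full 24 h cycle. Neither SAP 14.2 nor SAP 3.3 corrects for this.

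Three things are at stake:

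1. CL/F and Vz/F are primary PK endpoints (protocol 2.2.1; SAP 7.2), and protocol 1.7 says the PK results will help guide dosing recommendations.
2. The error grows with half-life. Protocol 3.1.1 allows that CKD3 may have different PK. If elimination is slower in CKD3, its CL/F is inflated more, which partly hides a true reduction.
3. Day 1 uses AUC(0-inf) and Day 7 does not. A drug with constant clearance would appear to clear faster by Day 7. That could be read as induction, or could hide inhibition.

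**Working it through.** **The plan's own PK figure, for scale.** Protocol 7.4 gives log-variances of 0.086 (Cmax) and 0.155 (AUC), with n = 8. The 90% range for the geometric mean is exp(±1.645 × √(variance/8)). This gives 84.3% to 118.6% for Cmax and 79.5% to 125.7% for AUC, matching the protocol. These figures do not test the point, but they show what a 10–20% systematic error sits beside. No value for Day 7 CL/F or its bias is stated.

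**Inputs.** Doses at 0 and 10 h every 24 h and the sampling times come from the protocol. Lixivaptan's half-life and absorption rate ka are not given and are assumed over a range. The only half-life information is that 96 h is about 4 half-lives of the longest-lived metabolite, so 96/4 = 24 h for that metabolite.

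**Direction.** By superposition, the steady-state AM interval collects these segments of the single-dose curve: 0–10, 24–34, … h from AM doses and 14–24, 38–48, … h from PM doses. It misses 10–14, 34–38, … h. Hence

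AUC(AM) = dose/(CL/F) − (missed segments) ≤ dose/(CL/F),

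and dose/AUC(AM) is never below CL/F, for any linear, time-invariant kinetics.

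**Size, one compartment with rapid input.** With k = ln 2/half-life, the missed fraction is sinh(2k)/sinh(12k), and

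reported/true CL/F = 1 / [1 − sinh(2k)/sinh(12k)].

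At 6 h, k = 0.1155, sinh(2k) = 0.2331 and sinh(12k) = (4 − 1/4)/2 = 1.875. The missed fraction is 0.1243, and 1/0.8757 = 1.142.

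| Assumed half-life | Rapid input, steady state | Oral, ka 0.5–2 per h, actual 14 doses |
|---|---|---|
| 2 h | +2.4% | +2.9% to +6.8% |
| 4 h | +9.9% | +10.9% to +15.5% |
| 6 h | +14.2% | +15.2% to +19.0% |
| 8 h | +16.4% | +17.2% to +20.3% |
| 12 h | +18.3% | +18.9% to +21.0% |
| 24 h | +19.5% | +21.2% to +22.4% |
| long limit | 12/10 = +20.0% | – |

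At a 1 h half-life with rapid input the error is 0.1%. At steady state with slower absorption the maximum is 21.1% (ka 0.5), 22.5% (ka 0.3) and 23.7% (ka 0.2).

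**Effect on a cohort contrast.** Only the ratio of the two biases matters. With rapid input, 8 h against 4 h gives 1.164/1.099 = 1.059, and 6 h against 3 h gives 1.142/1.064 = 1.073.

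**The replacement.** 2 × dose / [AUC(0-10) AM + AUC(0-14) PM] has zero error at steady state for every half-life. On the actual 14-dose schedule the error is at most about 1% (24 h half-life, accumulation not quite complete). With the protocol's sampling times and linear-up/log-down trapezoids, reported/true is about 1.01–1.04 for half-lives of 3–12 h and ka 0.5–2.

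**The case against.** The strongest reply accepts the direction and contests the importance.

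- **Unknown half-life.** The 20% is a limit, not an expected value, and near 2 h the error is a few percent. This stands.
- **Cohort comparison.** Much of the bias is shared. Even a doubled half-life distorts the ratio by only about 7%, against a precision range of 79.5% to 125.7% for one cohort's AUC. This also stands, but sampling error shrinks with more subjects and this error does not.
- **No formal decision.** The PK summaries are descriptive, no dose rule rests on CL/F, Cmax and the AUCs are unaffected, and a reader could recompute clearance from the listings. True, but a primary endpoint should not need recomputing by the reader.
- **Day 1 against Day 7.** The accumulation ratio RAUC(0-last) compares like AM windows. Where the bias is large, Day 1 AUC(0-inf) would often exceed the SAP's 30% extrapolation limit and be excluded. This is partial protection: the SAP does not say that Day 1 CL/F is excluded with it.
- **The replacement has limits.** It averages an AM dose taken after an overnight fast with a PM dose taken 2 h from meals, so bioavailability may differ. Trapezoid error can reach about 11% with very fast absorption and a 2 h half-life. Both are fair. The trapezoid error also affects the present formula: in that same case its overstatement goes from 2.6% with exact AUCs to 14.2% at the planned sampling times.

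Running AUC(0-last) on to Day 8 0 h does not rescue the rule. It would span two doses and roughly halve CL/F, and Table 5, organised by dosing interval, does not suggest it.

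**Conclusion.** The concern holds. As written, Day 7 CL/F is not a valid clearance for a 10 h/14 h regimen. Under linear, time-invariant kinetics it errs only upward, and nothing else in the documents corrects it. The size depends on a half-life the documents do not give: a few percent at 2 h, roughly 10–20% at 4–12 h, a limit of 20% at steady state with rapid input, and up to about 24% with slow absorption. Vz/F rises by the same factor if λz is unbiased. Separately, and whatever the half-life, Day 7 Vz/F is under-specified because no λz is assigned to that profile. Exposure measures and the Day 1 definition are not affected by this error.

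**What to change.** In PK/PD SAP Tables 3 and 5, and in protocol 7.1:

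1. Add AUC(0-10) for Day 7 AM as a named parameter ending at the pre-PM-dose sample, with a rule for a missing, late or unquantifiable 10 h sample, like the one already written for AUC(0-14).
2. Replace Day 7 AM CL/F with CL/F,ss = 2 × dose / [Day 7 AM AUC(0-10) + Day 7 PM AUC(0-14)].
3. Define Day 7 Vz/F as CL/F,ss divided by λz from the Day 7 PM profile.
4. Report neither parameter if either AUC is not evaluable, and state that CL/F,ss averages over the AM and PM dosing conditions.

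The cost is wording and one line of derivation code. No further samples are needed. A subject missing either Day 7 AUC loses CL/F and Vz/F for that day.
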